Study Protocol and Statistical Analysis Plan

Official Title: Relationship Between Electrical Impedance Tomography (EIT) Measurements and Parameters of Respiratory Status in Very Preterm Infants: An Observational Cohort Study

ClinicalTrials.gov Identifier: NCT06609135

Sponsor: [name]

Responsible Party: [name], University of Massachusetts, Worcester

Document Date: June 20, 2023

1. Study Overview

This is a prospective, single-center, observational cohort study conducted at the UMASS Memorial Medical Center NICU. The study investigates the use of Electrical Impedance Tomography (EIT) to assess respiratory status in very preterm infants, and its potential predictive value for the successful discontinuation of respiratory support at key developmental timepoints.

2. Study Design and Participants

- Design: Prospective observational cohort
- Setting: UMASS Memorial Medical Center NICU, Worcester, MA
- Study Start: November 4, 2023
- Completion Date: August 31, 2024
- Enrollment: 20 infants

Inclusion Criteria:

- Infants born between 25+0 and 29+6 weeks gestational age
- Admitted to UMass NICU

Exclusion Criteria:

- Major congenital anomalies
- Severe hemodynamic instability

3. Interventions and Devices

- Device: Sentec LuMon Electrical Impedance Tomography (EIT) system
- Device: Sentec Digital Monitoring System (transcutaneous CO₂ monitor)

EIT and CO₂ monitoring were performed at least twice weekly, ideally daily, starting from consent through NICU discharge.

4. Study Procedures

EIT monitoring began at 28+0 weeks PMA or 7 days postnatally (whichever came later), and was repeated weekly until NICU discharge. Sessions lasted 3 hours and were timed between feedings to reduce motion artifacts. Data were stored securely after each session.

5. EIT Metrics and Analysis

EIT data were analyzed breath-by-breath to derive the following parameters:

- FLS (Fraction of Lung Signal) – proxy for lung recruitment
- GI (Global Inhomogeneity Index) – indicator of ventilation uniformity
- CoV, EELI, and EILI were evaluated but not selected due to variability and artifacts GI was post-processed by Sentec; FLS was computed in-breath using standard software.

6. Study Outcomes

Primary Outcome

- Association of FLS and GI at 31+0 weeks PMA with successful CPAP discontinuation at 32+0 weeks PMA

Secondary Outcomes

1. Prediction of CPAP discontinuation at 33+0 weeks PMA based on EIT metrics at 32+0 weeks
2. Association of metrics at 34+0 weeks PMA with CPAP independence by 36+0 weeks
3. Exploratory:
 - Correlation between EIT and transcutaneous CO₂ levels
 - Correlation with time to full oral feeds
 - Association with BPD status at 36+0 weeks PMA

7. Statistical Analysis Plan

- T-tests for continuous variables (e.g., FLS, GI vs. CPAP outcomes)

- Fisher's exact tests for categorical demographic characteristics
- Missing data were handled via complete case analysis
- No imputation was applied
- Sample size (n=20) limits power; analyses are considered exploratory

8. Limitations

- Missing data due to timing of enrollment and technical failures
- Only 3/6 weaned infants and 8/14 non-weaned infants had usable data at 31 weeks
- At 33 weeks: 4/14 missing; at 36 weeks: 3/10 missing
- Measurement variability due to EIT belt placement, gel quality, motion, and interference
- Small sample size limits statistical power and generalizability
- Demographic imbalance (e.g., GA, weight) not controlled

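### Does the June 2023 header date misrepresent FLS and GI as chosen before the data were seen?

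*Combined protocol and SAP*

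**What the plan says.** The title block gives "Document Date: June 20, 2023". Section 2 (Study Design and Participants) gives "Study Start: November 4, 2023" and "Completion Date: August 31, 2024", with an enrollment of 20.

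Section 5 (EIT Metrics and Analysis) keeps two measures, FLS and GI. Of the other three it says "CoV, EELI, and EILI were evaluated but not selected due to variability and artifacts". Section 6 (Study Outcomes) then makes the retained pair the primary outcome: "Association of FLS and GI at 31+0 weeks PMA with successful CPAP discontinuation at 32+0 weeks PMA".

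Section 7 (Statistical Analysis Plan) reports the missing-data approach as already carried out, "Missing data were handled via complete case analysis", and gives the status of the work: "Sample size (n=20) limits power; analyses are considered exploratory".

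Section 8 (Limitations) contains data from the conduct of the study: "Only 3/6 weaned infants and 8/14 non-weaned infants had usable data at 31 weeks", followed by missing counts of 4 of 14 at 33 weeks and 3 of 10 at 36 weeks.

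**The concern.** A document titled as a protocol and analysis plan, and dated before the study opened, invites the reader to take its primary outcome as fixed in advance. Here that outcome names two of five EIT measures that were looked at. If the date is wrong for this text, it does not support that reading.

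What would be at stake is the standing of the primary result. Choosing two of five measures on signal quality, without sight of the CPAP outcome, does no harm to a later comparison by outcome. Choosing them after seeing which ones separated weaned from non-weaned infants would make nominal p-values too small. The document does not say when the choice was made, on which recordings, or whether outcome was known, so a wrong date could hide the second situation behind the appearance of the first.

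**Working it through.** **Inputs.** Document date June 20, 2023 (title block); study start November 4, 2023, completion August 31, 2024 and enrollment 20 (section 2); 6 weaned with 3 usable, 14 non-weaned with 8 usable (section 8); five measures considered, two kept (section 5).

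**1. Are the section 8 counts realised data?** 6 + 14 = 20, which reproduces the stated enrollment. Usable at 31 weeks: 3 + 8 = 11, and 11/20 = 55%. These are observed counts for the whole cohort, not projections.

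**2. Can they date from June 2023?**
- June 20 to November 4, 2023: 10 + 31 + 31 + 30 + 31 + 4 = 137 days.
- November 4, 2023 to August 31, 2024: 26 + 31 + 31 + 29 + 31 + 30 + 31 + 30 + 31 + 31 = 301 days.
- Document date to completion: 137 + 301 = 438 days.

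They cannot. Text holding these counts was written after the study began.

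**3. Does the text rely on the date?** Read side by side, sections 5 to 8 do not. No sentence calls FLS and GI prespecified. Section 5 discloses the three discarded measures and gives a reason that concerns signal quality, not association with outcome. Sections 3, 4, 5 and 7 use the past tense throughout, so a reader can see that this is a retrospective write-up.

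**4. Can a size be put on the harm?** Only by assumption. The plan states no significance level. With 0.05 per measure and independent measures, the chance of at least one false positive is 1 − 0.95² = 9.8% for two and 1 − 0.95⁵ = 22.6% for five. The larger figure applies only if all five were tested against outcome and the choice followed the results, which the document does not show. Independence is also doubtful for measures taken from the same recordings. Neither figure describes this study.

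**5. Would reporting the discarded measures by outcome group help?** Suppose they were usable in the same 3 and 8 infants. For a pooled two-sample t interval with 3 + 8 − 2 = 9 degrees of freedom, the 95% half-width in SD units is 2.262 × √(1/3 + 1/8) = 2.262 × 0.677 = 1.53. An interval of about ±1.5 SD, on measures already judged prone to artifact, would not tell a reader whether the selection was fair.

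**The case for a change.** The strongest case for acting is that the correction is cheap and the ambiguity is real. The exploratory label is justified by sample size, not by the timing of the metric choice, and section 6 still uses the word primary for a pair whose selection is undated. With only 11 infants contributing, 3 of them weaned, a reader has good reason to ask whether the pair was fixed beforehand. A sentence on when, and on which recordings, the other three were dropped would answer that.

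This much stands: the header date does not belong to this text, nobody should cite it as evidence of prespecification, and such a sentence would be useful in the report.

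The rest does not carry. Withdrawing a claim of prespecification has no object, because the document makes none. Labelling the choice post hoc would depend on facts that the document does not give. The date may have been carried forward from a version written before the study. Title and signature pages are not in the available text, so the absence of a version history here says little. Evaluation of the discarded measures might also refer to work before this cohort, although none is mentioned.

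**Conclusion.** No change to the plan is called for. The date error is certain on the document's own figures: 137 days before start and 438 days before completion, against counts for 20 of 20 infants. It is a clerical slip in the header. The missing timing of the metric choice is a gap in description that the authors can fill when they report the study.

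No outcome, test, analysis set or missing-data rule would differ with the right date in place, and no effect on error rates or estimates has been shown. Adding results for the three discarded measures does not follow from a date error, and at roughly 3 against 8 infants it would gain nothing.

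This rests on two readings. The stated study dates are taken as correct, and the signal-quality reason in section 5 is taken at face value because nothing in the document contradicts it. Evidence that the pair was chosen with CPAP outcomes in view would reopen the question, but the document contains none.

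### Secondary outcome 1 is worded as prediction, but the only method named for it is a t-test, which gives no estimate of discrimination and no interval for one

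*Combined protocol and SAP*

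**What the plan says.** Section 1 gives as one purpose of the study to examine, for EIT, "its potential predictive value for the successful discontinuation of respiratory support at key developmental timepoints".

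Section 6 then uses two different terms. Secondary outcome 1 is "Prediction of CPAP discontinuation at 33+0 weeks PMA based on EIT metrics at 32+0 weeks". The primary outcome is "Association of FLS and GI at 31+0 weeks PMA with successful CPAP discontinuation at 32+0 weeks PMA", and secondary outcome 2 is "Association of metrics at 34+0 weeks PMA with CPAP independence by 36+0 weeks".

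Section 7 names two tests. The first is "T-tests for continuous variables (e.g., FLS, GI vs. CPAP outcomes"; the second is Fisher's exact test, for categorical demographics only. It adds "Missing data were handled via complete case analysis" and "Sample size (n=20) limits power; analyses are considered exploratory". Section 8 reports "At 33 weeks: 4/14 missing; at 36 weeks: 3/10 missing".

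The document contains no ROC curve, AUC, sensitivity, specificity, cut-off, regression model or confidence interval.

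**The concern.** Prediction of a yes/no outcome from a continuous measurement asks how well the measurement sorts individual infants. A t-test asks whether two group means differ. Its p-value depends on both separation and sample size, so it does not measure separation and says nothing about how precisely separation is known.

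At stake is the reading of one secondary result. With about 10 infants, a p-value reported under an outcome called prediction would not show the reader that the data are compatible with anything from no useful separation to almost complete separation. The primary outcome and secondary outcome 2 are worded as associations, so a comparison of means fits them and this point does not concern them.

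**Working it through.** The plan states no power, alpha, effect size or AUC, so there is no figure of its own to reproduce.

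**Inputs from the document**
- Infants weaned and not weaned in the 31-week line of Section 8: 6 + 14 = 20, which matches enrolment.
- Infants in the 33-week line: 14, of whom 4 missing, so 14 − 4 = 10 usable under complete-case analysis.

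**Assumptions**
- The 4 missing refer to the 32-week EIT values that feed the 33-week outcome. The text does not say so; the case of all 14 usable is shown below.
- The split of usable infants by CPAP outcome is not given, so 1 vs 9 to 5 vs 5 is shown.
- The observed AUC is not given; 0.80 is used for illustration.

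**Step 1: interval for the AUC.** The score-type (Newcombe) 95% interval is the set of all A with (a − A)² ≤ 1.96² × V(A). Here a is the observed AUC, m and n are the group sizes, k = (m + n)/2 − 1, and

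V(A) = A(1 − A) × [1 + k(1 − A)/(2 − A) + kA/(1 + A)] / (mn).

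With 10 infants, k = 4. Check at 4 vs 6, a = 0.80, lower limit A = 0.422:
- A(1 − A) = 0.2439
- bracket = 1 + 1.465 + 1.187 = 3.652
- V = 0.2439 × 3.652 / 24 = 0.0371
- 1.96 × √0.0371 = 0.378, which equals 0.80 − 0.422.

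**Step 2: when the interval would exclude 0.5.** At A = 0.5 the bracket is 1 + 2k/3 = 3.667, so V(0.5) = 0.25 × 3.667/(mn) = 0.9167/(mn). The lower limit passes 0.5 when a > 0.5 + 1.96 × √V(0.5). Without ties, an AUC can only be a whole number divided by mn, so the smallest attainable value is what counts.

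| Split | 95% CI at AUC 0.80 | Threshold | Smallest attainable AUC above it |
|---|---|---|---|
| 1 vs 9 | 0.261–0.976 | 1.126 | none |
| 2 vs 8 | 0.354–0.963 | 0.969 | 16/16 = 1.00 |
| 3 vs 7 | 0.400–0.956 | 0.909 | 20/21 = 0.952 |
| 4 vs 6 | 0.422–0.952 | 0.883 | 22/24 = 0.917 |
| 5 vs 5 | 0.429–0.951 | 0.875 | 22/25 = 0.88 |

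These thresholds show the imprecision. They are not proposed as a criterion.

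**Step 3: all 14 usable.** At AUC 0.80 the interval runs from 0.371–0.960 (2 vs 12) to 0.487–0.939 (7 vs 7). It still includes 0.5 at the most favourable split.

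**Step 4: what a t-test result implies.** Under normality and equal variance, AUC = Φ(d/√2). At exactly p = 0.05 two-sided, d = t × √(1/m + 1/n). With 8 degrees of freedom t = 2.306, which gives:
- 5 vs 5: d = 1.46, AUC 0.85
- 4 vs 6: d = 1.49, AUC 0.85
- 3 vs 7: d = 1.59, AUC 0.87
- 2 vs 8: d = 1.82, AUC 0.90.

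The same p-value with equal groups corresponds to AUC 0.675 at n = 40 and 0.58 at n = 200, so a p-value does not fix discrimination. At 4 vs 6, the AUC of 0.85 at p = 0.05 has a Newcombe interval of 0.47–0.97.

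**Step 5: choice of interval.** The Wald interval with the Hanley–McNeil standard error, at AUC 0.80 and 5 vs 5, is 0.51 to 1.00 after capping, against 0.429–0.951 for the score-type interval. The method therefore has to be named. In simulation (equal-variance binormal, 40,000 replicates, 2 vs 8 to 5 vs 5, true AUC 0.70 to 0.90) the score-type interval covered between about 93.5% and 97%.

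**The case against.** The strongest case against runs as follows. The mismatch turns largely on one word in a short plan. The analyses are declared exploratory and limited in power, and Section 8 repeats the limits on power and generalizability. An AUC on 10 infants will say little, and it could be approximated from group means and SDs.

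Much of this lowers the consequence, and the grading reflects it. It does not supply what is missing. The exploratory label does not estimate discrimination. The approximation needs normality and equal variance, which about 10 infants cannot verify, and the plan does not specify it. Nor is the word isolated, since Section 1 gives predictive value as a purpose.

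Three stronger readings are tempting, and the document does not support them:

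- *A small p-value could hide weak separation.* That happens in large samples. With 10 infants, p = 0.05 already implies an observed AUC of about 0.85 or more (Step 4). What stays hidden is the width of the interval.
- *The primary outcome and secondary outcome 2 share the defect*, because Section 1 speaks of several timepoints. Section 6 words both as associations, and a mean comparison answers that.
- *An AUC interval excluding 0.5 would justify calling the result prediction, and one including 0.5 would not.* That names the outcome by its result and makes a significance test the criterion for prediction. Excluding 0.5 does not show useful discrimination.

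A fair point also stands on the split. The denominators fall from 14 at 33 weeks to 10 at 36 weeks, which suggests that 4 infants weaned in between. If so, the usable weaned group is at most 4 and 5 vs 5 cannot occur. This is an inference, so the full range is shown; it points towards the wider intervals.

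**Conclusion.** The point holds and is minor. For secondary outcome 1, the stated aim is prediction and the only named method cannot report predictive performance or its uncertainty. With 10 usable infants and an assumed AUC of 0.80, the 95% interval is between 0.951 − 0.429 = 0.522 and 0.976 − 0.261 = 0.715 wide, depending on the split. With 14 it is still between 0.939 − 0.487 = 0.452 (7 vs 7) and 0.960 − 0.371 = 0.589 (2 vs 12).

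The sizes rest on the assumed AUC, the unknown split and the reading of the 33-week missing-data line. The mismatch between wording and method rests on none of them. This is not a finding about power, which the plan already concedes.

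**What to change.** In Section 7, add one sentence for secondary outcome 1 only: report the AUC of FLS and the AUC of GI at 32+0 weeks for CPAP discontinuation at 33+0 weeks, each with a score-type (Newcombe) 95% confidence interval and the usable number in each outcome group. Label both as exploratory and post hoc, because the text already reports realised missingness. Read them descriptively, with no cut-off at 0.5.

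If the sponsor does not want to report discrimination, reword secondary outcome 1 as an association, in line with the other two CPAP outcomes. That choice should hold whatever the result.

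The cost is one sentence and a few lines of code on existing data. The downside is that the intervals will be very wide: the change shows the imprecision, adds no power and leaves the result post hoc.
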